5.4 Scheduled visits

The visits will be made at baseline, at 6 and 9 months of follow-up, not knowing to which group the patient belongs. The key will be opened only at the end of the second treatment period in order to assess the initial effects (after 9 months).

After screening, the patients enrolled will make a baseline visit during which they will be randomized into one of two groups. The visits will take place 6 and 9 months after the baseline visit.

At the baseline and each visit a complete ophthalmic examination will be performed, including the following assessments: corrected visual acuity, biomicroscopy, indirect ophthalmoscopy, measurement of intraocular pressure with Goldmann applanation tonometer, field of vision testing, recording of PERG and VEP, imaging of the optic nerve and retinal nerve fibre layer with OCT.

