Based on known preliminary data (Parisi et al, 2008), considering the implicit time P100 of the VEP and a power value = 90% ($\alpha = 5\%$) it is deemed reasonable to include in the study $N = 11$ observations (eyes tested) per group. The sample number has been calculated based on the difference in the implicit time P100 of the VEP measured after 60 days of treatment with Cisticoline for oral suspension compared to the baseline of 15 ms (Baseline P100: mean 141 ms, a standard deviation; P100 at 60 days: mean 126 ms, a standard deviation: 9.8 ms).

To summarise, the size from the sample estimated on the basis of the primary objective (visual acuity) is $N= 5$; the size from the sample estimated on the basis of secondary objectives (PERG and VEP) is $N=12$ and $N=11$, respectively.

Considering the larger sample size ($N=12$, PERG), and assuming the presence of outliers and the potential voluntary withdrawal from the study by patients, the sample is increased by 30%, so it is considered appropriate to reach $N=16$ observations (eyes tested) per group (NAION Treated with Cisticoline and NAION not treated).

In this calculation of the sample, it is not possible to estimate a priori the sample number relative to the secondary objective – point 3 (see Point 2.2), as data in the literature are not currently available regarding possible changes in the structure of nerve fibres and the optic nerve (assessed by OCT) following treatment with Cisticoline.

The calculation procedure was carried out using the Minitab v.12.7 and Gpower 3.1 programmes, assuming that the averages and standard deviations of all the parameters considered come from two independent samples: Patients with NAION in baseline condition and patients with NAION after 60 days of treatment with Cisticoline in oral suspension (Parisi et al, 2008).

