9.2 General methodology

Data from repetitions of visual acuity tests, PERG, VEP, OCT will be expressed as the average difference between two recordings obtained during separate sessions + / - the standard deviation of this difference. The 95% confidence limits of the test-retest variability will be established by assuming a normal distribution of the data, after verification using the Anderson-Darling and Kolmogorov-Smirnov tests, calculating the average of the differences and the relative standard deviations.

For each group (NAION Control eyes and NAION eyes Treated with Cisticoline), differences in visual acuity values, PERG and VEP and OCT responses measured at 6 and 9 months from

baseline will be assessed using ANOVA and the $p < 0.05$ value will be considered significant. Multiple comparisons will be made using the Tukey and Games-Howell methods, establishing the value of the error rates at 5%.

Correlations between the electric-physiological measurements (PERG/VEP) and field of view measurements, normalized in logarithmic value, both at Baseline and at each follow-up time, for each group will be performed using Pearson's test and the $p < 0.05$ value will be considered significant.

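### Section 9.2 compares repeated visits of the same eyes with Games-Howell, an independent-groups method, and names no within-eye error term for the ANOVA or Tukey

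*Combined protocol and SAP*

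**What the plan says.** Section 9.2 sets the analysis up separately by arm: "For each group (NAION Control eyes and NAION eyes Treated with Cisticoline"). Within each arm it takes "differences in visual acuity values, PERG and VEP and OCT responses measured at 6 and 9 months from" baseline, and the sentence ends "baseline will be assessed using ANOVA" with a 5% significance level. It then adds: "Multiple comparisons will be made using the Tukey and Games-Howell methods, establishing the value of the error rates at 5" per cent.

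Section 5.4 shows that the time points are repeated visits by the same patients: "The visits will be made at baseline, at 6 and 9 months of follow-up".

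The type of ANOVA is not given. Neither section 9.1 nor section 9.2 mentions a repeated-measures, paired or mixed model, a within-eye error term, or a sphericity condition for the visit comparisons.

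Section 9.1 describes its sample-size calculation as "assuming that the averages and standard deviations of all the parameters considered come from two independent samples". The two samples it then names are patients with NAION at baseline and patients with NAION after 60 days of treatment. By the account of the pilot study in section 1.2, these are the same treated patients before and after.

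**The concern.** An eye with poor acuity at baseline will usually have poor acuity at 6 and 9 months. In a within-eye change that stable difference between eyes cancels. In an independent-groups comparison it stays in the error term.

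Games-Howell builds its standard error from the two separate variances and has no covariance term. For these contrasts it is therefore the wrong method, whichever ANOVA comes before it. Section 9.1 suggests that the authors may have had an independent-samples framework in mind for pre-post data.

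Two things are at stake. The error rate delivered would not be the stated 5%. Small real changes would also be missed more often than 16 eyes per arm requires. The second matters because the primary objective (section 2.1) is maintenance and stabilisation of acuity, and section 10.1 describes unchanged PERG, VEP and nerve-fibre thickness as maintenance. An insensitive test makes a small real deterioration harder to see.

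**Working it through.** **Inputs from the documents.** 16 eyes per arm; three visits; acuity SD 0.122 (baseline) and 0.107 (day 60) logMAR; planned acuity change 0.35 logMAR; PERG change 0.38 microvolts with SDs 0.29 and 0.25; power 90%, alpha 5%.

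**Assumptions, not in the documents.** Visit correlation r, shown from 0 to 0.7 and equal for all pairs of visits; two-sided testing; an illustrative change of 0.05 logMAR present at both follow-up visits; one eye per patient.

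**Step 1: the plan's own figures.** Average SD for acuity = √((0.122² + 0.107²)/2) = 0.115, so d = 0.35/0.1147 = 3.05.
- Acuity: a two-independent-sample t calculation needs 4 eyes per group (power 94.5%) and has 98.7% power at the stated 5.
- PERG: d = 0.38/0.271 = 1.40, which gives 12 eyes (power 90.7%), as stated.
- VEP: the stated 11 is obtained if the baseline SD, which is not legible in the text, is 9.8 to 10 ms.
- Final size: 12 × 1.3 = 15.6, rounded to 16.

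The sizes reproduce to within one eye on the independent-samples basis that section 9.1 describes.

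**Step 2: does pairing overturn those sizes?** The SD of change is √(s₁² + s₂² − 2·r·s₁·s₂). A paired t calculation needs 5, 4, 4 and 4 eyes for acuity at r = 0, 0.3, 0.5 and 0.7. For PERG it needs 13, 10, 8 and 6. All are below 16, so the sample size does not fall on this point.

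**Step 3: the error term.** With equal SDs, the true standard error of a change is SD·√(2(1 − r)/n). The independent-groups version is SD·√(2/n), too large by a factor 1/√(1 − r), which is 1.41 at r = 0.5.

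The Tukey half-width with independent-group error is q(3, 45)·SD/√16 = 3.43 × 0.115/4 = 0.099 logMAR, whatever r is. With within-eye error it is q(3, 30)·SD·√(1 − r)/√16 = 3.49 × 0.115 × √(1 − r)/4.

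**Step 4: error rate and power.** Familywise error comes from simulation under no change (20,000 or more trials per correlation). For power with the within-eye error, the noncentrality is 16 × 0.05² × (2/3)/(0.115² × (1 − r)). At r = 0.5 this is 0.02667/0.00661 = 4.03, and with F on 2 and 30 degrees of freedom the power is 38%. Power with independent-group error is simulated.

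| r (assumed) | Familywise error, Games-Howell | Familywise error, Tukey with within-eye error | Tukey half-width, independent / within-eye (logMAR) | Overall power for 0.05 logMAR, independent / within-eye |
|---|---|---|---|---|
| 0 | 4.8% | 4.9% | 0.099 / 0.100 | 21% / 21% |
| 0.3 | 1.6% | 5.1% | 0.099 / 0.084 | 15% / 28% |
| 0.5 | 0.5% | 5.0% | 0.099 / 0.071 | 11% / 38% |
| 0.7 | 0.06% | 5.0% | 0.099 / 0.055 | 6% / 59% |

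Simulated values move slightly between runs: Games-Howell at r = 0.5 gave 0.4% to 0.5%, and the within-eye power there gave 38% to 39%. Tukey with an independent-group error behaves almost the same as Games-Howell.

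**Step 5: the planned effect.** For 0.35 logMAR, even the independent-groups ANOVA has essentially 100% power. For 0.15 logMAR at r = 0.5 it has 99%. The loss is confined to changes much smaller than the one planned for.

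**The case against.** Much of the case on the other side stands.

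- **Tukey.** A reader might infer that both named procedures are wrong here. The documents do not support that for Tukey, which is valid after a repeated-measures ANOVA with the within-eye error under sphericity. Section 9.2 does not say which ANOVA is meant, so for Tukey the error term is missing rather than shown to be wrong.
- **Confidence limits.** A reader might infer that the plan's confidence limits for change in acuity are wrong. It specifies none. Its only limits are described thus: "The 95% confidence limits of the test-retest variability will be established by assuming a normal distribution of the data". They are obtained by "calculating the average of the differences and the relative standard deviations", which is a paired calculation. The half-widths in the working apply only to intervals that the multiple-comparison procedures would produce.
- **Section 9.1.** Its independence assumption is a sample-size input. It hints at how the authors thought, but it does not define the error term in section 9.2.
- **Change scores.** The wording could mean an ANOVA on changes from baseline, where stable between-eye variance has already cancelled. Games-Howell still fails on that reading. The 6- and 9-month changes share a baseline, so with equal visit correlations their covariance is SD²(1 − r) against a variance of 2·SD²(1 − r), a correlation of 0.5 that the method ignores.
- **Stabilisation.** A reader might infer that a non-significant result will be declared stabilisation. No section states such a rule. The lost sensitivity is relevant to the aim, but that step is inference.
- **Inputs.** The correlation and the 0.05 logMAR change are not in the documents, and at r = 0 there is no penalty. Section 5.1 expects some patients to contribute both eyes. Treating fellow eyes as independent can push the error rate the other way, so the percentages are not this trial's actual error rate.

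**Conclusion.** The concern holds in a limited form. Games-Howell is unsuitable for comparing visits of the same eyes, and section 9.2 leaves the error term of its ANOVA and Tukey comparisons open.

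If independent-group error terms are used, the departure is conservative: familywise error falls from 5% to roughly 1.6%, 0.5% and 0.06% at assumed correlations of 0.3, 0.5 and 0.7. Power for a 0.05 logMAR change at 0.5 drops from about 38% to about 11%. These figures assume 16 eyes, three visits, SD 0.115, equal correlations and no fellow eyes.

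A reader might go further and conclude that the plan risks false claims of benefit from this source, or that the trial is wrongly sized. Neither follows. A conservative test does not create false positives, power for the planned 0.35 logMAR change is untouched, and 16 eyes exceeds every paired requirement in the range shown.

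**What to change.** In section 9.2, delete Games-Howell and replace the unspecified ANOVA with one repeated-measures mixed model per outcome. Baseline should be one of the modelled visits and not also a covariate. The model needs a within-eye correlation across visits, and a patient random effect where both eyes are enrolled. If every patient contributes one eye, separate patient and eye effects cannot be told apart and only the within-eye correlation is needed. Take multiplicity-adjusted visit contrasts from this model.

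A simpler alternative is paired contrasts between visits with a multiplicity adjustment. Where both eyes of a patient enter, these would still need to allow for the fellow eye.

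In section 9.1, state that the pilot baseline and day-60 values are paired, and show the calculation over an assumed range of visit correlation or SD of change.

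The cost is SAP wording and one stated correlation assumption. No extra data, visits or patients are needed, and SAS, named in section 13, can fit such a model.

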9. STATISTICAL ANALYSIS

9.1 Sample size

The sample size is estimated based on the primary objective: 'assessment of stabilisation and/or improvement of visual acuity' (see section 2.1.).

This calculation is based on known preliminary data (Parisi et al, 2008), in which visual acuity was assessed through Early Treatment Diabetic Retinopathy Study (ETDRS) cards and the acquired value has been expressed in LogMAR (logarithm of the minimum angle of resolution).

Based on these known preliminary data (Parisi et al, 2008), and considering a power value = 90% ($\alpha = 5\%$) it is deemed reasonable to include in the study $N = 5$ observations (eyes tested) per group.

The sample size has been calculated based on the difference in visual acuity measured in patients with NAION after 60 days of treatment with Citicoline in oral suspension compared to the baseline of 0.35 LogMAR (baseline visual acuity: mean 0.621 LogMAR, a standard deviation: 0.122 LogMAR; visual acuity at 60 days: mean 0.271 LogMAR, a standard deviation: 0.107 LogMAR).

However, based on the secondary objective-point 2 (see section 2.2) 'to determine in patients with NAION the potential for neuroenhancement related to the administration of Citicoline oral solution. This will be achieved through functional condition assessments (PERG/VEP) measured after treatment with Citicoline compared to the condition at the time of recruitment", it is considered appropriate to assess the sample size taking into account the known preliminary data (Parisi et al, 2008) in which they were analysed:

- a) changes in the functionality of retinal ganglion cells by measuring the Amplitude P50-N95 (measured in microvolts) obtained by recording the ERG from Pattern (PERG).
- b) changes in optic nerve function by measuring Implicit Time P100 (measured in milliseconds, ms) obtained by recording Visual Evoked Potential (VEP).

Based on known preliminary data (Parisi et al, 2008), considering the P50-N95 amplitude of the PERG and a power value = 90% ($\alpha = 5\%$) it is reasonable to include in study $N = 12$ observations (eyes tested) per group. The sample number has been calculated based on the difference in the P50-N95 amplitude of the PERG measured after 60 days of treatment with Citicoline for oral suspension compared to the baseline of 0.38 microvolts (Baseline P50-N95: mean 0.92 microvolts, a standard deviation: 0.29 microvolts; P50-N95 at 60 days: mean 1.30 microvolts, a standard deviation: 0.25 microvolts).

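### The 90% power stated for PERG at 12 eyes per group belongs to one unadjusted comparison; under the Tukey/Games-Howell pairwise rule in section 9.2 it is about 81–83% if visits are uncorrelated, and 90% needs 15 evaluable eyes

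*Combined protocol and SAP*

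**What the plan says.** Section 9.1 (Sample size) sizes visual acuity, PERG and VEP separately and lets the largest number set the trial. That is PERG: "it is reasonable to include in study $N = 12$ observations (eyes tested) per group". The target is 90% power with alpha 5%. The inputs are the pilot values, "Baseline P50-N95: mean 0.92 microvolts, a standard deviation: 0.29 microvolts" and "P50-N95 at 60 days: mean 1.30 microvolts, a standard deviation: 0.25 microvolts", a difference of 0.38 microvolts. The calculation is described as "assuming that the averages and standard deviations of all the parameters considered come from two independent samples". No adjustment for multiple comparisons is mentioned. The 12 eyes are then raised by 30%, for outliers and withdrawals, to 16 per group.

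Section 9.2 (General methodology) compares, within each group, the values at 6 and 9 months with baseline by ANOVA at p<0.05, and adds: "Multiple comparisons will be made using the Tukey and Games-Howell methods, establishing the value of the error rates at 5" percent. Section 5.4 fixes three visits: baseline, 6 months and 9 months.

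**The concern.** Tukey and Games-Howell both use the studentized range. With three means, their critical values are larger than that of a single t comparison at 5%. If 9.1 used the single-comparison value, its 90% describes a test that 9.2 does not use for pairwise differences.

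This touches the trial size because PERG sets it. The 30% increase is meant to cover lost eyes. If the stricter rule absorbs part of that increase, fewer eyes can be lost before power for the size-setting parameter drops below the stated level. Secondary objective 2 in section 2.2 (PERG/VEP after treatment against enrolment) depends on that pairwise contrast, since the overall ANOVA does not show which visit differs.

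**Working it through.** **Inputs (section 9.1).** PERG difference 1.30 − 0.92 = 0.38 microvolts; SDs 0.29 and 0.25; alpha 5%; target power 90%; 12 eyes per group before the 30% increase. Sidedness is not stated. From section 9.2: Tukey and Games-Howell at 5%. From section 5.4: three visits, hence three pairwise comparisons within a group.

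**Step 1: reproduce the plan's figure.**
- Common SD = √((0.29² + 0.25²)/2) = √0.0733 = 0.2707.
- d = 0.38/0.2707 = 1.404.
- Noncentrality = d√(n/2); at n = 12 this is 1.404 × √6 = 3.44.
- Two-sided t test, 22 df, critical value 2.074: power 90.7%. At n = 11 it is 87.9%.

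So 12 is the smallest n reaching 90%, and the printed figure reproduces. A one-sided test would give 10. The sizing is therefore one unadjusted two-sided comparison.

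**Step 2: keep every input and change only the critical value.** The new value is q(0.95; 3 means, df)/√2, with df = 3(n − 1) for Tukey and the Welch df for Games-Howell. At n = 12 it is 2.454 (33 df) for Tukey and 2.516 (21.5 df) for Games-Howell.

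| Evaluable eyes per group | Unadjusted t | Tukey | Games-Howell |
|---|---|---|---|
| 12 | 90.7% | 83.2% | 81.3% |
| 13 | 93.0% | 86.6% | 85.0% |
| 14 | 94.7% | 89.4% | 88.1% |
| 15 | 96.0% | 91.6% | 90.6% |
| 16 | 97.0% | 93.5% | 92.6% |

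First n at or above 90%: 12 unadjusted, 15 under either adjusted rule. Eyes per group that can be lost from 16: 16 − 12 = 4 as sized, 16 − 15 = 1 under 9.2.

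**Step 3: simulation at n = 12.** Third-visit SD set to 0.27 and third-visit mean to 0.92, 1.11 or 1.30; all three are assumptions, since 9.1 has only two time points. With uncorrelated visits, Tukey gives about 83% and Games-Howell about 81%, agreeing with Step 2. The documents give no within-eye correlation, so a range is shown for an ordinary ANOVA:

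| Assumed correlation | Tukey | Games-Howell |
|---|---|---|
| 0 | 83% | 81% |
| 0.3 | 87% | 84% |
| 0.5 | 90% | 87% |
| 0.7 | 93% | 90–91% |

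A third-visit SD of 0.25 instead raises the Tukey figures by about 1 to 2 points. The overall ANOVA F test, with uncorrelated visits, has about 85–94% power, depending on the 9-month mean.

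**Step 4: the other parameters.** Visual acuity: difference 0.35 LogMAR, SDs 0.122 and 0.107, d = 3.05. At its own n = 5, power is 98.7% unadjusted, 97.4% by Tukey and 95.1% by Games-Howell. VEP: the baseline SD does not appear in the text available, so its N of 11 cannot be checked and no adjusted figure is given.

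**The case against.** The strongest reply is that the trial plans 16 eyes per group, not 12. At 16, power under the stricter rule is about 93%, above the target. That stands: 81–83% arises only if the whole 30% allowance is lost. A reader might infer that the trial as planned has only 81–83% power for PERG, or that it needs 15 × 1.3 = 19.5 eyes per group. The documents support neither. The 16 eyes suffice as long as no more than one per group is lost.

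Second, the same eyes are measured three times, so zero correlation is unlikely. This also stands. The 81–83% rests on the independence that 9.1 itself assumes and so is comparable with the stated 90%; it is not a forecast of actual power. Section 9.2 says only ANOVA and does not exclude a repeated-measures form. With a repeated-measures Tukey test, simulated power at 12 eyes is about 94% or more for correlations of 0.3 or above.

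Third, 9.2 attaches its significance statement to the ANOVA and does not use the word family. Control over the set of comparisons is inferred from the methods named, and the three-visit family from the within-group wording. If all six group-by-visit cells were one family, Tukey power at 12 eyes would be about 69%, but nothing in 9.2 calls for that reading. The shortfall concerns the pairwise step, not the overall F test.

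Fourth, PERG is a secondary outcome. A reader might infer that the primary analysis is underpowered for this reason; Step 4 shows that it is not.

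**Conclusion.** The mismatch is real and minor. The arithmetic in 9.1 for PERG is correct for the test it assumes, but 9.2 names a stricter test for pairwise differences. On 9.1's inputs, with uncorrelated visits and a three-visit family within each group, the stated 90% at 12 evaluable eyes becomes about 83% (Tukey) or 81% (Games-Howell). A PERG effect of the assumed size would then be missed in about 17–19% of trials against 9% as sized, but only if four eyes per group are lost. With 15 or 16 evaluable eyes the target is met. The practical consequence is a thinner margin for losses, one eye per group instead of four, and positive within-eye correlation would ease even that.

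**What to change.** In 9.1, add: the 90% power for PERG at 12 eyes per group refers to one unadjusted two-sided comparison at 5%; under the Tukey/Games-Howell rule of 9.2, and assuming uncorrelated visits, 12 evaluable eyes per group give about 81–83%, and 90% holds only if at least 15 of the 16 eyes per group are evaluable. In 9.2, state that the comparison family for each parameter is the three visits within each group.

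Testing one PERG contrast unadjusted would also make the two sections agree, but it is not recommended here. It would remove multiplicity control from the parameter that sets the trial size, and it would first have to be settled whether the contrast is within or between groups.

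The cost is two or three sentences and no additional patients. The only downside is a less favourable stated power.

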5.6 Efficiency parameters

- For the VA examination, the visual acuity values will be recorded for distance and near vision corrected with the best optical correction.
- For the visual field examination, the following parameters will be recorded: mean deviation (MD), pattern standard deviation (PSD), number of points, with $p < 5\%$ and $< 1\%$ in the pattern deviation map and the total deviation map.
- Each PERG examination will record the following parameters: latency P50 and amplitude P50-N95.

- The following parameters will be recorded for each VEP test: latency N75 and P100, amplitude N75-P100 and P100-N145
- For each OCT imaging session the following parameters will be recorded: the average thickness of the retinal nerve fibre layer and the thickness divided according to sectors.
- At baseline and at each control visit (6 and 9 months) a complete eye examination will be performed including the following assessments: corrected visual acuity, biomicroscopy, indirect ophthalmoscopy, measurement of intraocular pressure with Goldmann applanation tonometer, field of vision testing, recording of PERG and VEP, imaging of the optic nerve and retinal nerve fibre layer with OCT.

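### PERG/VEP–visual field correlations are split by arm even at baseline and each is judged at p<0.05, with no named pairs and no multiplicity rule

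*Combined protocol and SAP*

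**What the plan says.** Section 9.2 (General methodology) describes the analysis as "Correlations between the electric-physiological measurements (PERG/VEP) and field of view measurements, normalized in logarithmic value", to be done "both at Baseline and at each follow-up time, for each group will be performed using" Pearson's test. The criterion is p<0.05 for each correlation. The visits are baseline, 6 and 9 months (section 5.4).

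Section 9.2 does not say which PERG, VEP or field parameters are paired. Section 5.6 lists what is recorded:

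- PERG: "Each PERG examination will record the following parameters: latency P50 and amplitude P50-N95", so 2 parameters.
- VEP: "latency N75 and P100, amplitude N75-P100 and P100-N145", so 4 parameters.
- Visual field: "mean deviation (MD), pattern standard deviation (PSD), number of points", the points being counted at two probability levels on two deviation maps, so 2 indices and 4 counts.

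The Tukey and Games-Howell methods in section 9.2 come directly after the ANOVA and compare means. They do not apply to a set of Pearson tests. No sentence labels the correlations exploratory. Correlation of function with visual field changes is part of secondary objective 2 (section 2.2) and is repeated in section 5.5.

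**The concern.** Two features of the rule work against each other.

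First, a baseline correlation within one arm answers no treatment question, because nobody has yet been treated. Splitting there gives up half the eyes and makes every estimate less precise.

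Second, every correlation carries a 5% significance label and the set of correlations is not fixed in advance. Chance findings accumulate with the number of pairs examined, and the pairs can be chosen after the data are seen.

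The combination has a particular consequence. With 16 eyes per arm, a moderate correlation of the same true size in both arms will often be significant in one and not in the other. A reader could take that as an effect of citicoline on the function–field relation when there is none.

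**Working it through.** **The plan's own figure: 16 eyes per group (section 9.1).** The inputs for PERG P50-N95 are a difference of 0.38 microvolts and SDs of 0.29 and 0.25.

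- Common SD = √((0.29² + 0.25²)/2) = 0.271; standardised difference = 0.38/0.271 = 1.40.
- Two independent means, two-sided α 0.05, noncentral t: n = 12 per group gives power 0.907, so the stated 12 reproduces.
- 12 × 1.3 = 15.6, rounded to 16. This also reproduces.

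So each by-arm correlation has 16 planned eyes and a pooled one has 32. The sample size was not based on correlations, and no expected r is given.

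**Critical |r|.** Two-sided 5% (sidedness is not stated, so this is assumed): r_crit = t/√(t² + n − 2).

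- n = 16: t = 2.145, r_crit = 2.145/√(4.600 + 14) = 0.497.
- n = 32: t = 2.042, r_crit = 2.042/√(4.171 + 30) = 0.349.

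**Power, Fisher z.** Power ≈ Φ(atanh(r)·√(n − 3) − 1.96), assuming independent eyes and no losses.

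- r = 0.40, n = 16: Φ(0.4236 × 3.606 − 1.96) = Φ(−0.43) = 33%. With n = 32: Φ(0.4236 × 5.385 − 1.96) = Φ(0.32) = 63%.
- r = 0.50, n = 16: Φ(0.5493 × 3.606 − 1.96) = Φ(0.02) = 51%. With n = 32: Φ(0.5493 × 5.385 − 1.96) = Φ(1.00) = 84%.
- r = 0.70, n = 16: 88%. Simulation of bivariate normal data gives 90%.

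**Number of tests.** Electrophysiology parameters × field parameters × 3 visits × 2 arms; expected chance findings if no association exists = 0.05 × tests.

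| Reading of section 9.2 | Tests | Expected by chance |
|---|---|---|
| P50-N95 and P100 with MD (2 × 1) | 12 | 0.6 |
| P50-N95 and P100 with MD and PSD (2 × 2) | 24 | 1.2 |
| All 6 with MD (6 × 1) | 36 | 1.8 |
| All 6 with MD and PSD (6 × 2) | 72 | 3.6 |
| Everything in section 5.6 (6 × 6) | 216 | 10.8 |
| As above plus retino-cortical time from section 5.5.2 (7 × 6) | 252 | 12.6 |

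The expected counts do not need the tests to be independent of one another, only that each has a true 5% level.

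**Significant in exactly one arm.** If the true r is the same in both arms and each arm has power p, the chance is 2p(1 − p). Simulated power with 16 eyes is 0.346 at r = 0.40, 0.532 at 0.50 and 0.733 at 0.60.

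- r = 0.40: 2 × 0.346 × 0.654 = 45%.
- r = 0.50: 2 × 0.532 × 0.468 = 50%.
- r = 0.60: 2 × 0.733 × 0.267 = 39%.

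This applies to each pair, however many pairs are tested.

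**The case against.** The strongest reply is that 216 tests is not in the plan. Section 5.6 lists what is recorded, not what is correlated. Elsewhere the protocol singles out P50-N95 amplitude and P100 (sections 9.1 and 10.1) and calls MD and PSD the main field indices (section 5.5.1). On that reading there are 24 tests, or 12 with MD alone. This stands: a reader might infer from section 5.6 that 216 tests are planned, but section 9.2 supports only a range. What remains is that the plan does not choose within that range.

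It is also tempting to say that chance findings are certain. They are not. On the narrow readings about one or fewer is expected. On the full cross the parameters overlap and the same eyes return at each visit, so false positives cluster. The counts also assume no association anywhere, whereas sections 1.4 and 5.5.2 cite significant correlations between these measures in glaucoma.

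Low power is likewise not general. It applies to r below about 0.6.

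The pooled power figures assume no losses, independent eyes and an unadjusted 5% level. If losses use up the whole 30% allowance, 24 pooled eyes give 49/71% at r = 0.40/0.50, against about 25/38% with 12 eyes in one arm (same formula). Bilateral patients would reduce the effective number further. The advantage of pooling remains, at a lower level.

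Finally, within-arm baseline values have some use as a reference for the same arm's later correlations, and section 9.2 plans no comparison of correlations between arms. Both are fair. By-arm values can still be shown as estimates, and the risk of a treatment reading lies in how the labels would be read, not in a planned analysis.

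**Conclusion.** The point holds for a secondary analysis. Section 9.2 splits the baseline correlations by arm without need and attaches an unadjusted 5% label to an unspecified set of pairs.

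- At baseline the split raises the critical |r| from 0.35 to 0.50 and lowers power at r = 0.40/0.50 from about 63/84% to 33/51%, assuming 32 independent eyes and no losses. Correlations of 0.7 or more remain well powered at about 90%.
- The tests could number up to about 216, with about 11 chance findings if no association exists, if all parameters in section 5.6 are crossed. Narrower readings give 12 to 72 tests and 0.6 to 3.6 chance findings.
- A moderate correlation (r of 0.4 to 0.5) that is the same in both arms would be significant in exactly one of them about 45 to 50% of the time.

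A reader might infer that the trial's main result is compromised. The documents do not support that: the primary objective is visual acuity (section 2.1), and neither it nor the sample size depends on these correlations.

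**What to change.** Reword the correlation paragraph of section 9.2:

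1. At baseline, estimate the correlations on both arms pooled, with a method that allows for two eyes from one patient.
2. Name two main pairs: PERG P50-N95 amplitude with MD, and VEP P100 with MD. The first members are the sponsor's own sample-size variables, and MD is one of its main field indices.
3. Report all other correlations, including the by-arm ones at 6 and 9 months, as r with a 95% CI and no significance label.
4. State that no treatment conclusion will be drawn from a correlation that is significant in one arm only.

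If only the two main pairs at pooled baseline keep a test, the expected number of chance findings is 2 × 0.05 = 0.1. The plan should say whether those two share the 5% level. If each is tested at 2.5%, the pooled power at r = 0.40/0.50 becomes about 52/76% (1.96 replaced by 2.24 in the formula above).

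The cost is wording only: no new data, visits or patients. The downside is that the remaining correlations become descriptive.
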